2 STUDY OBJECTIVES

2.1 Primary Objective

The primary objective of this study is to determine the proportion of patients achieving both complete remission and seronegativity for ANCA at 6 months. Complete remission is defined as a Birmingham Vasculitis Activity Score for Wegener's Granulomatosis (BVAS/WG) of 0 without glucocorticoids beyond the prescribed prednisone taper. Seronegativity for ANCA is defined as a negative test for antibodies directed against serine proteinase 3 (i.e., a negative PR3-ANCA assay).

2.2 Secondary Objectives

The secondary objectives of this study are:

- To compare the proportion of subjects who achieve sustained complete remission at month 6 after administration of obinutuzumab or rituximab. ***Complete remission is defined as BVAS/WG = 0 without glucocorticoids***
- To compare the proportion of subjects who achieve sustained complete remission at month 12 after administration of obinutuzumab or rituximab.
- To compare the proportion of subjects who achieve sustained complete remission at month 18 after administration of obinutuzumab or rituximab.

- To compare the time to treatment failure through month 18 by administration of obinutuzumab or rituximab; Patients will be considered treatment failures if the glucocorticoid dose has to be increased at any point during the 18-month study period because of a disease relapse. ***Disease relapse is defined as an increase in the BVAS/WG of ≥ 1 point accompanied by a decision on the part of the investigator to increase treatment for PR3-AAV***
- Time to treatment failure. ***Treatment failure is defined as the event when the glucocorticoid dose has to be increased at any point during the 18-month study period because of a disease relapse.***

Follow-up in the trial will continue until all patients have been followed for 18 months.

2.3 Exploratory Objectives

The exploratory objectives are to compare between the two treatment groups for following outcomes:

- The number of disease relapses as defined in section 2.2.
- The Glucocorticoid Toxicity Index (GTI) scores (Cumulative Worsening Score and Aggregate Improvement Score) over time;
- The cumulative glucocorticoid dose administered orally;
- The cumulative glucocorticoid dose administered via intravenous or oral route;
- The number of severe relapses. ***Severe relapse is defined as the occurrence of life- or organ-threatening disease manifestation(s); marked by an increase in the major BVAS/WG items of ≥ 3 at months 6, 12, 18 and the investigator deems standard treatment for severe disease is necessary.***
- The changes from baseline in Vasculitis Damage Index (VDI) over time;
- The time to clinical remission;
- The changes in estimated glomerular filtration rate (eGFR) based on CKD-Epi equation without correcting for race;
- The proportion of patients achieving and maintaining complete peripheral blood B cell depletion (CD19+) at each study visit by high sensitive flow cytometry (HSFC)
 - Proportion of patients achieving B-cell depletion (HSFC) at specified timepoints.
 - Proportion of patients with sustained B-cell depletion (HSFC) over time.
- The kinetics of ANCA:
- Time to negative testing for ANCA
- Time to recurrence of a positive test for ANCA (after negative testing);
- The kinetic of recurrence of PR3-specific (autoantigen-specific) B cells after B cell depletion
- The changes from baseline on AAV patient reported outcome (AAV-PRO) assessment over time
- Vasculitis Clinical Research Consortium (VCRC) Granulomatosis with polyangiitis/ microscopic polyangiitis (WG/MPA) disease activity and transition assessment over time

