- To compare the time to treatment failure through month 18 by administration of obinutuzumab or rituximab; patients will be considered treatment failures if the glucocorticoid dose has to be increased because of a disease relapse either during the prednisone taper or after the remission is achieved. A disease relapse is defined as an increase in the BVAS/WG of 1 point or more accompanied by a decision on the part of the investigator to increase treatment for PR3-AAV. Time-to-treatment failure will be compared between treatments using the log-rank test; Kaplan-Meier plots of time to treatment failure through 18 months will be generated for each randomized treatment group; patients not experiencing treatment failure will be censored at last known follow-up for these analyses.

The exploratory objectives are to be analyzed as comparison between the two treatment arms. Descriptive statistics will be reported by treatment group.

The exploratory biomarker samples and results will be analyzed and reported separately.

Study Conduct:

The clinical trial will be conducted in compliance with regulations (21 CFR 312, 50, and 56), guidelines for Good Clinical Practice (ICH Guidance E6), and in accordance with general ethical principles outlined in the Declaration of Helsinki; informed consent will be obtained from all participating patients; the protocol and any amendments will be subject to approval by the designated IRB prior to implementation, in accordance with 21 CFR 56.103(a); and subject records will be stored in a secure location and subject confidentiality will be maintained. The investigator will be thoroughly familiar with the appropriate use of the study drug as described in the protocol and Investigator's Brochure. Essential clinical documents will be maintained to demonstrate the validity of the study and the integrity of the data collected. Master files should be established at the beginning of the study, maintained for the duration of the study and retained according to the appropriate regulations.

Date of Original Approved Protocol: Version 11JAN2021

LIST OF ABBREVIATIONS AND DEFINITIONS OF TERMS

Abbreviations	
AAV	ANCA-associated vasculitides
ADCC	antibody-dependent cellular cytotoxicity
AE	adverse event
ANCA	antineutrophil cytoplasmic antibody
BVAS/WG	Birmingham Vasculitis Activity Score for Wegener's Granulomatosis
CD20	pan-B cell antigen
CDC	complement-dependent cytotoxicity
CLL	chronic lymphocytic leukemia
CRF	case report form

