3 INVESTIGATIONAL PLAN

3.1 Overall Study Design and Plan

This is a double-blind, randomized, active controlled multi-center phase 2 study to evaluate the efficacy and safety of obinutuzumab for the treatment of PR3-AAV. The study will enroll approximately 30 patients who have clinical diagnoses of either granulomatosis with polyangiitis or microscopic polyangiitis. All patients enrolled must have positive serum assays for PR3-ANCA, manifestations of severe disease, and a BVAS/WG of ≥ 3 (Thompson et al., 2020).

Severe disease is defined as at least one major BVAS/WG item or a BVAS/WG ≥ 3 and the need for standard therapy for severe disease as per investigator. Patients who are positive for serum assays for ANCA directed against myeloperoxidase (MPO-ANCA) will be excluded.

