9.2 Determination of Sample Size

PRRR is an exploratory proof-of-concept study to evaluate the potential utility of obinutuzumab for the treatment of PR3-ANCA associated vasculitis. We anticipate the proportion of patients in the obinutuzumab group that will achieve complete remission and ANCA negativity is 0.55 and the proportion of patients in the rituximab group that will achieve complete remission and ANCA negativity is 0.30; the planned sample size of 30 patients in two equal size groups is not powered to test the hypothesis that obinutuzumab is superior to rituximab. No sensitivity analyses (e.g., to account for missing data) and no adjustment for multiple comparisons will be conducted. Nominal p-values will be used to examine any trends in the endpoint.

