9.3.2 Modified Intention-to-Treat Analysis Set

All subjects who are included in the intention-to-treat analysis set (ITT), have received any amount of the study drug will be included in the modified intention-to-treat (mITT) analysis set. The mITT will be the primary analysis set used for the efficacy endpoint analyses.

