9.8 Other Assessments or Analyses

The exploratory objectives are to compare:

- the number of relapses, defined as an increase in the BVAS/WG by at least one point accompanied by an increase in the intensity of treatment;
- the Glucocorticoid Toxicity Index (GTI) scores (Cumulative Worsening Score and Aggregate Improvement Score) over time;
- the cumulative glucocorticoid dose;
- the number of severe relapses, defined as the occurrence of life- or organ-threatening disease manifestation(s) or marked by an increase in the BVAS/WG of ≥ 3 and the investigator deems re-treatment is required;
- the changes from baseline in Vasculitis Damage Index (VDI) over time;
- the time to clinical remission;

- the changes in estimated glomerular filtration rate (eGFR);
- the proportion of patients achieving and maintaining complete peripheral blood B cell depletion (CD19+) at each study visit using high-sensitivity flow cytometry (HSFC);
- the kinetics of ANCA:
- Time to ANCA negativity
- Time to ANCA recurrence;
- the kinetic of recurrence of PR3-specific (autoantigen-specific) B cells after B cell depletion
- the changes from baseline on AAV patient reported outcome (AAV-PRO) assessment over time
- VCRC WG/MPA disease activity and transition assessment over time

The mechanistic study results will be analyzed and reported separately.

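### Time to ANCA recurrence compares the arms only among patients who turned ANCA-negative after randomisation, so the comparison can be biased in either direction

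*Combined protocol and SAP*

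**What the plan says.** Section 2.3 opens with "The exploratory objectives are to compare between the two treatment groups for following outcomes" and, under the kinetics of ANCA, lists "Time to recurrence of a positive test for ANCA (after negative testing" (bracket closed in the source). The synopsis lists the same outcome, and section 9.8 shortens it to "Time to ANCA recurrence". On method, the Statistical Methods part of the synopsis says "The exploratory objectives are to be analyzed as comparison between the two treatment arms" and adds that descriptive statistics will be given by group.

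On entry status, section 3.1 states "All patients enrolled must have positive serum assays for PR3-ANCA". On analysis sets, section 9.3.2 states "The mITT will be the primary analysis set used for the efficacy endpoint analyses". No set is named for the exploratory outcomes. For this outcome, no section gives a time origin, a rule for patients who never turn negative, or a rule for results after open-label obinutuzumab. Section 9.1 refers to a separate full SAP, which is not among the documents reviewed.

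**The concern.** A patient who never tests negative cannot have a recurrence. Since all patients start positive, nobody is at risk of the event at randomisation, and the definition alone restricts the comparison to converters. ANCA negativity is half of the primary endpoint, and section 9.2 expects the arms to differ on that endpoint. If obinutuzumab converts patients whom rituximab would not have converted, the two groups of converters differ in kind as well as in treatment.

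Lasting seronegativity is central to the rationale: sections 1 and 3.3.4 argue that reaching ANCA negativity goes with long-term disease control. Yet no other planned outcome reports lasting ANCA negativity in all randomised patients. Time to negative testing measures onset. The remission endpoints at months 6, 12 and 18 in section 9.7 do not include ANCA.

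A smaller point concerns detection. Appendix 1 also schedules ANCA serum at unscheduled visits, which are prompted by signs or symptoms of recurring disease. An arm with more flares is tested more often and may have recurrence found sooner. The documents give no basis for sizing this, and the three-monthly draws limit it.

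**Working it through.** The plan gives no figure for this outcome, so there is none to reproduce.

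**Inputs from the documents**
- Section 9.2, for obinutuzumab: "We anticipate the proportion of patients in the obinutuzumab group that will achieve complete remission and ANCA negativity is 0.55". For rituximab it puts the corresponding figure at 0.30. These are rates of remission plus negativity at month 6, used here as stand-ins for conversion. Conversion alone cannot be lower than the composite.
- 30 patients, 1:1, so 15 per arm. Expected converters: 15 × 0.55 = 8.25 v 15 × 0.30 = 4.5.
- As Appendices 1 and 2 read, ANCA is first retested at month 6 and then every three months to month 18. That leaves 12 months in which to see recurrence.

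**Assumptions, not in the documents**
- 30% convert on either drug (common converters), and a further 25% convert on obinutuzumab only (extra converters).
- Recurrence is exponential, with a median of 12 months in common converters on rituximab: λ = ln 2 / 12 = 0.0578 per month.
- Extra converters recur k times as fast as common converters.

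**Formulas.** At rate r over 12 months, the recurrence risk is F = 1 − exp(−12r) and the mean ANCA-negative time is T = F / r. Per randomised obinutuzumab patient, events are 0.30 F(common) + 0.25 F(extra), and negative months are 0.30 T(common) + 0.25 T(extra). The apparent rate ratio is events divided by months, divided by λ.

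**Rituximab arm.** F = 0.50 and T = 0.50 / 0.0578 = 8.66 months. Per randomised patient: 0.150 events and 0.30 × 8.66 = 2.6 negative months.

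**No drug effect on recurrence (common converters at rate λ on both drugs)**

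| k | F, T in extra converters | Events | Negative months per randomised patient | 12-month recurrence in converters | Rate ratio |
|---|---|---|---|---|---|
| 0.5 | 0.293, 10.14 | 0.223 | 5.1 | 41% | 0.75 |
| 1 | 0.500, 8.66 | 0.275 | 4.8 | 50% | 1.00 |
| 1.5 | 0.646, 7.46 | 0.312 | 4.5 | 57% | 1.21 |
| 2 | 0.750, 6.49 | 0.338 | 4.2 | 61% | 1.38 |
| 3 | 0.875, 5.05 | 0.369 | 3.9 | 67% | 1.65 |

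Recurrence in converters is events / 0.55; the rituximab figure is 50%. For k = 2: events are 0.150 + 0.25 × 0.750 = 0.3375, months are 2.60 + 0.25 × 6.49 = 4.22, and the ratio is (0.3375 / 4.22) / 0.0578 = 1.38. For k above 1 the converter-only ratio goes against obinutuzumab, while negative months per randomised patient favour it in every row (3.9 to 5.1 v 2.6).

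**Obinutuzumab halves recurrence in all its converters.** Common converters have rate λ/2, so F = 0.293 and T = 10.14. Extra converters have rate kλ/2. The ratios are 0.50, 0.61, 0.71 and 0.88 for k = 1, 1.5, 2 and 3. For k = 2: events are 0.0879 + 0.125 = 0.213, months are 3.04 + 2.16 = 5.21, and the ratio is 0.71. The true effect in like patients is 0.50, so the benefit is understated but not reversed.

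**Halving in common converters only.** The ratios are 0.88, 1.02 and 1.23 for k = 1.5, 2 and 3.

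**Random error.** At k = 2 with no drug effect, expected recurrences are 15 × 0.3375 = 5.06 v 15 × 0.150 = 2.25. The standard error of the log ratio is √(1/5.06 + 1/2.25) = 0.80, so the 95% interval around 1.38 runs from about 0.3 to 6.7.

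**The case against.** The best case for leaving the plan alone has five parts.

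- **Direction.** A reader might infer that the comparison is biased against whichever drug converts more patients. The documents do not support that. It needs the extra converters to recur faster, and nothing in the protocol says they do. With equal recurrence there is no bias. With slower recurrence the bias favours obinutuzumab. The protocol also hypothesises deeper and longer B-cell depletion on obinutuzumab (sections 1 and 3.3.1), and with halved recurrence in all its converters the ratio stays below 1 across k = 1 to 3. This part stands.
- **Consequence.** A reader might infer that this result will shape the next trial. Section 9.5 ties future studies to the trend in the primary endpoint only. This also stands.
- **Weight.** The outcome is one of about a dozen exploratory items in a study declared not powered. It is reported descriptively, with no test or model named, and chance error exceeds the bias computed here. This limits the stakes. It does not turn converters into randomised groups, and both sections 2.3 and 9.8 still call the analysis a comparison.
- **Companion outcomes.** Time to negative testing starts from all patients, and the remission and treatment-failure endpoints use ITT and mITT. None of them measures how long ANCA negativity lasts.
- **Rescue.** An all-patient comparison has its own problem. Under section 3.1.2, treatment failures in either arm with detectable B cells are offered open-label obinutuzumab and stay in follow-up. Later negativity in the rituximab arm could then be produced by obinutuzumab. This is right, and the remedy must deal with it.

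**Conclusion.** The concern holds as a structural flaw. Followed as written, the plan compares subsets formed after randomisation by a process that the sponsor expects to differ between arms. It would understate or reverse an obinutuzumab benefit only if the extra converters recur faster. The no-effect ratios of 1.21 to 1.65, and the 0.61 to 0.88 seen under a halving whose true value is 0.50, illustrate this and do not predict it. They rest on composite rates standing in for conversion, on everyone who would convert on rituximab also converting on obinutuzumab, and on assumed exponential recurrence with a 12-month median. The likely sign is unknown.

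The importance is modest, since the result is exploratory and descriptive and the primary analysis is untouched. The change is still worth making, because it supplies the only all-patient measure of lasting ANCA negativity and costs little.

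**What to change.** In section 9.8 and the full SAP:

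1. Make the between-arm comparison of ANCA durability on all mITT patients, as (a) the proportion ANCA-negative at each of months 6, 9, 12, 15 and 18, and (b) the number of those five scheduled visits at which the patient is ANCA-negative, with 0 for never-negative patients. Give a between-arm difference and 95% CI for each.
2. For this analysis, count results after treatment failure or open-label obinutuzumab as not ANCA-negative, and show the as-observed results alongside. Cite one definition of treatment failure: section 3.1.2 includes other treatment prescribed for relapse, while section 9.7 names only a glucocorticoid increase.
3. State how missed visits are counted.
4. Report time to recurrence among converters by arm as description only, from scheduled draws, with a stated time origin and no between-arm inference.

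The cost is wording and some programming. The central ANCA draws at these visits are already scheduled, and section 9.1 leaves the full SAP open until the month-6 analysis.

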2.4 Safety Objectives

To determine the safety profile of patients administered obinutuzumab by assessing:

- Treatment emergent adverse events
- Treatment emergent serious adverse events
- Laboratory testing
- Glucocorticoid use related toxicity using Glucocorticoids Toxicity Index (GTI) 2.0
- Treatment emergent adverse events of special interest including:
 - Infusion related reactions (IRR)
 - Grade 3 or higher infections
 - Hepatitis B reactivation
 - Progressive multifocal leukoencephalopathy (PML)
 - Drug-related neutropenia
 - Drug-related thrombocytopenia
 - Gastrointestinal perforations
 - Worsening of pre-existing cardiac conditions.

3 INVESTIGATIONAL PLAN

3.1 Overall Study Design and Plan

This is a double-blind, randomized, active controlled multi-center phase 2 study to evaluate the efficacy and safety of obinutuzumab for the treatment of PR3-AAV. The study will enroll approximately 30 patients who have clinical diagnoses of either granulomatosis with polyangiitis or microscopic polyangiitis. All patients enrolled must have positive serum assays for PR3-ANCA, manifestations of severe disease, and a BVAS/WG of ≥ 3 (Thompson et al., 2020).

Severe disease is defined as at least one major BVAS/WG item or a BVAS/WG ≥ 3 and the need for standard therapy for severe disease as per investigator. Patients who are positive for serum assays for ANCA directed against myeloperoxidase (MPO-ANCA) will be excluded.

3.1.1 Remission Induction Period

Eligible patients will be randomly assigned in a 1:1 ratio to receive two doses of either rituximab or obinutuzumab (both drugs dosed at 1000 mg per infusion). Infusions will be given approximately two weeks apart, on day 0 and day 14. All randomized patients will be prescribed a specified glucocorticoid regimen. The glucocorticoid regimen will include one to three pulses of methylprednisolone (1000 mg each) starting on or within 10 calendar days of study day 0 followed by prednisone at a dose of 60 mg per day. The glucocorticoid dose will be tapered so that by week 2 of glucocorticoid treatment taper, the patients will take no more than 40 mg/day prednisone equivalent. All patients who have a remission without disease flares will be off glucocorticoids completely in 16 weeks. Patients will complete clinic visits at months 1, 2, 4 and 6 after the first infusion has been administered.

3.1.2 Maintenance Phase

Patients who respond to treatment and achieve clinical remission will enter the maintenance phase and be evaluated every 3 months after the 6-month primary outcome assessment for a total of 18 months from the first dose. Patients will be considered treatment failures if the glucocorticoid dose has to be increased either during the prednisone taper or after remission because of a disease relapse or if any other treatment for ANCA-associated vasculitis is prescribed to treat a disease relapse. The patients who experienced treatment failure with detectable B cells (≥ 5 cells/ μ l) will be offered open-label obinutuzumab accompanied by one to three intravenous methylprednisolone pulses (1000 mg each) starting on or within 10 calendar days of obinutuzumab followed by oral glucocorticoid dosing at the discretion of the investigator (but not to exceed the original specified glucocorticoid tapering regimen) to control the disease. Patients who experience a treatment failure and B cells are still depleted should be treated according to best medical judgment. Patients who respond to the re-treatment and achieve clinical remission will enter the maintenance phase and be evaluated every 3 months until the entire study completes. Any patient who experiences treatment failure should continue with study follow-up visits per the schedule of assessments through the end of study.

All patients will be followed until they will have completed 18 months of follow-up or withdraw from the study prematurely.

The specific visit schedule is presented in Section 7, [Table 5](#). The study design is illustrated in [Figure 1](#).

[figure not shown]

Figure -1 PRRR Study Design

3.1.3 Endpoint Analysis

The primary endpoint of comparing the proportion of patients who achieve complete remission and ANCA negativity will be conducted after all patients have completed the 6-month remission induction period. The data pertinent to the primary efficacy analysis will be source verified, locked and transferred to an independent statistician to perform the limited analysis. The statistical analysis plan will be developed and finalized prior to the analysis. This will be the only analysis to be conducted for the specified endpoint and the summary results without individual patient information will be available to a limited number of recipients. The investigators will continue to be blinded to the patient treatment assignment throughout the remainder of the follow-up period.

The 6-month analysis will be treated as an interim analysis with regard to the blinding and data handling. Since the treatment regimen will be completed after the second study drug infusion and the primary efficacy analysis is conducted once at the 6-month time point, no multiplicity adjustment will be used for the analysis.

